## 10 SAFETY ANALYSES

All safety summaries and listings will be performed using the SS. All safety variables will be listed and summarized by study part, treatment sequence (Sequence A/Sequence B), treatment (PSL+OC / OC alone / PSL alone) and time point, when applicable.

---

## 10.1 Extent of exposure

All study medication (OC and PSL) administration details will be listed by study part, treatment sequence, and study participant. The listing will include the date and time of administration of the morning and evening dose and total daily dose of medication.

Exposure data will be listed only.

## 10.2 Adverse events

All AEs will be coded using the MedDRA® and characterized as pre-treatment and treatment-emergent according to the intake of the study medications (PSL, OC).

Adverse events with a start date prior to the first dose of study medication will be defined as pre-treatment AEs. For sequence A, the first dose of PSL is given on Day 1. For sequence B, the first dose of OC is given on Day 1.

A treatment-emergent AE (TEAE) is defined as any AE with a start date/time on or after the first dose of study medication (OC or PSL) or any unresolved event already present before administration of study medication that worsens in intensity following exposure to the treatment. Where dates are missing or partially missing, AEs will be assumed to be treatment-emergent, unless there is clear evidence to suggest that the AE started prior to the first dose of study medication. Missing or partially missing dates for AEs will be handled as described in Section 4.2.4.

Adverse events will be attributed to the treatment (OC, PSL or OC+PSL) after which they start. Thus, in **part 1**, for study participants randomized in Sequence A, all AEs starting after the first intake of PSL through Day 13 (prior to OC intake) will be attributed to PSL, all AEs starting after OC intake on Day 13 through Day 34 (prior to OC intake) will be attributed to PSL+OC, and all AEs starting after OC intake on Day 34 through Day 41 will be attributed to OC. In **part 1**, for study participants randomized in Sequence B, all AEs starting after the OC intake on Day 1 through Day 18 (prior to PSL intake) will be attributed to OC, all AEs starting after PSL intake on Day 18 through Day 30 (prior to OC intake) will be attributed to PSL, and all AEs starting after OC intake on Day 30 through Day 43 will be attributed to OC+PSL. In **part 2**, for study participants randomized in Sequence A, all AEs starting after the first intake of PSL through Day 9 (prior to OC intake) will be attributed to PSL, all AEs starting after OC intake on Day 9 through Day 26 (prior to OC intake) will be attributed to PSL+OC, and all AEs starting after OC intake on Day 26 through Day 33 will be attributed to OC. In **part 2**, for study participants randomized in Sequence B, all AEs starting after the OC intake on Day 1 through Day 18 (prior to PSL intake) will be attributed to OC, all AEs starting after PSL intake on Day 18 through Day 26 (prior to OC intake) will be attributed to PSL, and all AEs starting after OC intake on Day 26 through Day 35 will be attributed to OC+PSL. AEs starting more than 168 hours post last dose of study medication will be attributed to the SFU Period. A schematic summary is shown below.

Study Part	Sequence	PSL alone	PSL + OC	OC alone	SFU
1	A	Day 1 – 13 (prior to OC intake)	Day 13 (after OC intake) – 34 (prior to OC alone intake)	Day 34 (after OC intake) - 41	42+
	B	Day 18 (after PSL intake) – Day 30 (prior to OC intake)	Day 30 (after OC intake) - 43	Day 1 – 18 (prior to PSL intake)	44+
2	A	Day 1 – 9 (prior to OC intake)	Day 9 (after OC intake) – 26 (prior to OC intake)	Day 26 (after OC intake) - 33	34+
	B	Day 18 (after PSL intake) – 26 (prior to OC intake)	Day 26 (after OC intake) – 35	Day 1 – 18 (prior to PSL intake)	36+

All AEs will be recorded in the CRF from the time of informed consent until study completion or termination. All AEs will be coded (see [Section 3.8](#)) and categorized by intensity (mild/moderate/severe) and relationship (related/not related) to study medication (PSL, PSL+OC, and OC) as judged by the Investigator.

All AE data will be listed by study part, treatment sequence, study participant number, start date, and time. The listings will include the following data pertaining to the AEs: start and end dates with relative days to study medication administration, duration, intensity, seriousness, relationship to study medication, action taken, and final outcome.

The number and percentage of study participants who experience TEAEs will be summarized by MedDRA SOC, PT, treatment sequence and treatment period.

Summaries of TEAEs will include the following:

- Overview of incidence of TEAEs (overview including number and percentage of study participants with any TEAEs, any serious AEs, TEAE of Special Interest, TEAEs leading to discontinuation, drug-related TEAEs, severe TEAEs and TEAEs leading to death; event counts will also be included)
- Incidence of TEAEs by maximum relationship
- Incidence of TEAEs by maximum intensity
- Incidence of non-serious TEAEs above reporting threshold of 5% of study participants

Summary tables will contain counts of study participants, percentages of study participants in parentheses and the number of events where applicable. A study participant who has multiple events in the same SOC and PT will be counted only once in the study participant counts but all events will be included.

In summaries including relationship, the following relationships will be summarized: 'Not related', 'Related'. Study participants who experience the same event multiple times will be included in the most related category for tabulations by maximum relationship. Events with missing relationship will be considered as 'Related' but recorded as missing in the listings.

In summaries including intensity, the following intensity categories will be summarized: 'Mild', 'Moderate', 'Severe'. Study participants who experience the same event multiple times will be included in the most severe category for tabulations by maximum intensity. Events with missing intensity will be considered as 'Severe' events for summary purposes but recorded as missing in the listings.

Incidence of Non-Serious TEAEs above reporting threshold of 5% of study participants will be reported by system organ class and preferred term.

Adverse event summaries will be ordered alphabetically by SOC and decreasing frequency of PT within SOC in the PSL+OC column for tables including event counts. For tables including only number and percentage of study participants, summaries will be ordered alphabetically by SOC and decreasing incidence of PT within SOC in the PSL+OC column.

Listings of AEs and TEAEs will include the following:

- All AEs
- Incidence of all TEAEs
- All Serious AEs
- Discontinuation due to AEs.

All listings (except incidence of all TEAEs) will be presented by study part, treatment sequence (Sequence A/Sequence B) study participant and treatment period (PSL+OC/OC alone) and will include the SOC, PT, reported term, onset date/time and outcome date/time of the event (including relative days), the event duration (derived), time to onset (derived), pattern of event, intensity, relationship, action taken, outcome and AEs that led to discontinuation. TEAEs and SAEs will be flagged.

The listing of incidence of all TEAEs will be presented by study part and treatment sequence and will include intensity, relationship, severity, number of subject reporting a least one TEAE within SOC/PT, number of individual occurrences of TEAEs and site-participant number.

Additional summary tables of fatal, serious and discontinuation due to TEAEs by relationship will be produced if more than one of these events occurs.

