8.3.6 Psychiatric and Mental Status

The psychiatric and mental status of study participants will be closely monitored. Assessment of specific domains of psychiatric and cognitive symptoms will be performed by a staff member trained in the identification of psychiatric symptoms. The Psychiatric and Mental Status assessment will be performed according to the Schedule of Activities. The parameters that will be evaluated cover orientation, attention, memory, mood, calculus, behavior, and thinking or feeling. These parameters will be assessed as normal or abnormal and then determined whether clinically significant. If present and abnormal, psychiatric symptoms, mental impairment, and behavioral problems will be assessed as to whether they are clinically significant.

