8.4.1 Time period and frequency for collecting AE and SAE information

All AEs and SAEs will be collected from the signing of the ICF and at the time points specified in the Schedule of Activities.

Medical occurrences that begin before the start of study medication, but after obtaining informed consent will be recorded on the Medical History/Current Medical Conditions section of the eCRF, not the AE section.

All SAEs will be recorded and reported to the Sponsor or designee within 24 hours, as indicated in Appendix 3 (Section 10.3). The Investigator will submit any updated SAE data to the Sponsor within 24 hours of it being available.

The Investigator is specifically requested to collect and report to UCB (or its representative) any SAEs (even if the Investigator is certain that they are in no way associated with the study medication), up to 30 days from the end of the study for each study participant, and to also inform study participants of the need to inform the Investigator of any SAE within this period. Serious AEs that the Investigator thinks may be associated with the study medication must be reported to UCB regardless of the time between the event and the end of the study.

The method of recording, evaluating, and assessing causality of AE and SAE and the procedures for completing and transmitting SAE reports are provided in Appendix 3 (Section 10.3).

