### 3.6 Treatment assignment

It is expected that study participants will receive treatments as per the randomized treatment sequence and hence the analyses will be based on the randomized treatment. If a study participant was randomized but not dosed in any treatment period, the study participant results will be reported under the randomized treatment group. For safety analyses based on the SS, study participants will be classified according to the medication that was actually received.

Except for PK, concomitant medications, and adverse events, tables will be presented separately for each study part by randomized Treatment Sequence (Sequence A: PSL+ OC followed by OC alone and Sequence B: OC alone followed by PSL+OC) and overall. Listings will be presented by study part, randomized treatment sequence, and study participant number. PK summaries will be presented by study part, treatment period (OC alone and OC+PSL), and analyte (EE, LN; PSL and its metabolites). Concomitant medication and adverse event tables will be presented separately for each study part by treatment (OC alone, PSL alone, and OC+PSL).

A detailed schematic diagram of the study is provided in [Table 2-2](#) and [Table 2-3](#).

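### Part 1 TEAE percentages are tabulated by treatment over windows of 7 to 21 days with no person-time, which can inflate PSL+OC and makes OC alone depend on sequence

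*SAP*

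**What the plan says.** SAP 3.6 sets the layout: "Concomitant medication and adverse event tables will be presented separately for each study part by treatment (OC alone, PSL alone, and OC+PSL". The treatments are columns of one table, since SAP 10.2 orders rows by "decreasing frequency of PT within SOC in the PSL+OC column". On content, SAP 10.2 says: "Summary tables will contain counts of study participants, percentages of study participants in parentheses and the number of events where applicable". Under SAP 10.1, exposure is listed only. No rate per unit of time is planned.

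SAP 10.2 then fixes the onset windows. For OC alone in Part 1, Sequence A, "AEs starting after OC intake on Day 34 through Day 41 will be attributed to OC"; in Sequence B, "all AEs starting after the OC intake on Day 1 through Day 18 (prior to PSL intake) will be attributed to OC". A 168-hour limit sends later events to the safety follow-up column, but it runs only from the last dose of the whole study, not from the last dose of the first period. Sequence A's washout therefore counts to PSL+OC, and Sequence B's counts to OC alone.

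On collection, Protocol 8.4.1 says: "All AEs and SAEs will be collected from the signing of the ICF and at the time points specified in the Schedule of Activities". Protocol 8.3.6 says: "The Psychiatric and Mental Status assessment will be performed according to the Schedule of Activities".

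The SAP is not consistent about sequence. Section 10.2 has TEAEs "summarized by MedDRA SOC, PT, treatment sequence and treatment period", and the opening of Section 10 also lists sequence. Section 3.6 and the Section 13 table give AEs by treatment and overall only.

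**The concern.** The chance that a participant has at least one event grows with the time she is watched. Columns with different windows can show different percentages when the daily rate is identical. Here one column label also covers different time by sequence: OC alone is one week in A, and two and a half weeks including the washout in B.

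TEAE incidence is the secondary endpoint for PSL tolerability, and OC alone is the only off-PSL column in the same participants. Under SAP Section 1 only Part 1 will be reported, as a subset of outputs for trial registries, where percentages may be read without the window definitions beside them.

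Observation also differs in kind. PSL-alone time is wholly in clinic, while most OC-alone time is at home. The psychiatric and mental status evaluation follows PSL dosing. Protocol 10.3.1 counts clinically significant abnormal safety assessments as AEs, so this schedule can feed the tables.

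**Working it through.** **Check of the SAP's own figures.** SAP 3.2.2 gives 20 days of exposure in Part 1. PSL on Days 1–19 (A) or 18–36 (B) is 19 days, plus 1 OC-only day = 20. The 168-hour rule gives Day 34 + 7 = 41 (A) and Day 36 + 7 = 43 (B). Both match SAP 10.2.

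**Window lengths.** Limits come from SAP 10.2, counted from morning dose to morning dose. The exception is PSL+OC in B, which ends 168 hours after the Day 36 evening dose. Clinic days come from Protocol Tables 1-4 and 1-5, with discharge on Day 20 or 21 (A) and Day 37 or 38 (B).

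| Column | A (days) | B (days) | Mean | In clinic, A+B |
|---|---|---|---|---|
| PSL alone | 13 − 1 = 12 | 30 − 18 = 12 | 12.0 | 24/24 = 100% |
| PSL+OC | 34 − 13 = 21 | 13.5 | 17.25 | 15/34.5 to 17/34.5 = 43–49% |
| OC alone | 41 − 34 = 7 | 18 − 1 = 17 | 12.0 | (2+3)/24 = 21% |

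For 7 + 7 completers the participant-days are 7 × 24 = 168 for PSL alone, 7 × 34.5 = 241.5 for PSL+OC and 7 × 24 = 168 for OC alone.

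**Length alone.** Assume one constant daily rate h under every treatment, and full capture. Expected incidence is 1 − exp(−h × days), averaged over two equal sequences. The documents give no rate, so h is an assumption. At h = 0.05:

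- PSL alone: 1 − exp(−0.60) = 45.1%.
- PSL+OC: A 1 − exp(−1.05) = 65.0%; B 1 − exp(−0.675) = 49.1%; mean 57.0%.
- OC alone: A 1 − exp(−0.35) = 29.5%; B 1 − exp(−0.85) = 57.3%; mean 43.4%.

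| h per day | PSL alone | PSL+OC | OC alone, pooled | OC alone, A / B |
|---|---|---|---|---|
| 0.02 | 21.3% | 29.0% | 20.9% | 13.1% / 28.8% |
| 0.05 | 45.1% | 57.0% | 43.4% | 29.5% / 57.3% |
| 0.10 | 69.9% | 80.9% | 66.0% | 50.3% / 81.7% |

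PSL+OC exceeds PSL alone by 8 to 12 points with no true difference. OC alone differs between sequences by 16 to 31 points. Pooled PSL alone and OC alone differ by only 0.4 to 3.9 points.

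**Ascertainment.** During the washout, AE recording is scheduled only at re-admission (Day 33 in A, Day 17 in B). If out-of-clinic events were captured at 75%, 50% or 25% (assumptions, h = 0.05), pooled OC alone would show 37.0%, 29.7% or 21.4% against 45.1% for PSL alone. PSL+OC would fall too: at 50% capture it would be about 46–47%, which nearly cancels its length excess.

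**Psychiatric evaluation.** Counting scheduled evaluations per participant gives about 12–13 in PSL alone and 6–7 in PSL+OC (one more in B if the follow-up visit falls on Day 43). OC alone has none in B and at most one in A, if the follow-up visit falls on Day 41. None is scheduled on the OC-only clinic days (Days 34–36 in A, Days 1–3 in B).

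**The case against.** The AE tables are descriptive, with no test between columns. Event counts are planned as well as percentages. The listings carry onset times, so a reader could rebuild any window and derive the denominators. The programme was stopped, and only a subset of outputs will be reported. All of this is correct and limits the consequence. It does not supply the missing denominator where the percentages are read, and event counts without participant-days do not correct for length.

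Three stronger readings are tempting, and the documents do not support them.

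- A reader might infer that PSL alone and OC alone must differ by construction. In the pooled Part 1 table both windows average 12 days, so length contributes almost nothing. What remains is ascertainment. Its direction is plausible, but washout events can still be reported at re-admission, so capture is delayed rather than absent, and no capture figure is given.
- A reader might infer that psychiatric events are looked for only on PSL. In Sequence B a C-SSRS is scheduled on Day 17, inside the OC-alone window. In Sequence A the follow-up visit includes a psychiatric evaluation and may fall on Day 41. The accurate statement is narrower: no evaluation on the OC-only clinic days.
- A reader might want every PSL statement to rest on the 48 hours after each OC dose. That window starts after 12 days of PSL and leaves out titration and taper, while Protocol 2.3 reports AEs easing over the first days of dosing and asks for extra vigilance in titration and taper. It could understate the burden of PSL.

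**Conclusion.** The point holds for window length and, with a narrower claim, for ascertainment. At an assumed constant 5% per day with full capture, length alone puts PSL+OC about 12 points above PSL alone, and OC alone about 28 points higher in Sequence B than in A. These sizes rest on the assumed rate, on equal rates across treatments and on completers; the window lengths themselves are fixed by SAP 10.2. The sequence effect is largest in any by-sequence table, and whether such tables are planned is itself unclear. The PSL-alone versus OC-alone contrast can be affected only through clinic stay and the psychiatric evaluation schedule, by an amount the documents do not allow one to state. This is a worthwhile, low-cost improvement to descriptive tables. It does not invalidate the safety analysis.

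**What to change.** In SAP 10.2:

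1. Show participant-days at risk and the TEAE rate per participant-day beside each percentage, by treatment and by sequence.
2. Show washout time beyond 168 hours after the last dose of a period in its own column. For 14 completers this gives PSL alone 168, PSL+OC 14 × 13.5 = 189, OC alone 14 × 7 = 98 and late washout 7 × 7.5 + 7 × 10 = 122.5 participant-days, which sum to the same 577.5 as now. The split makes the sequences equal but sets 12 days of PSL alone against 7 of OC alone (45.1% against 29.5% at 5% per day), so the rates must accompany the percentages.
3. As a supplement only, tabulate TEAEs starting within 48 hours after each OC dose, with PSL (Days 13–15 in A, 30–32 in B) and without (Days 34–36 in A, 1–3 in B). Label it a comparison of steady-state PSL+OC with OC alone that excludes titration and taper.
4. Footnote that the psychiatric and mental status evaluation was not scheduled on the OC-only clinic days, so psychiatric TEAEs are not comparable between the PSL and OC-alone columns. Neither rates nor the 48-hour table removes this imbalance.
5. Reconcile SAP 3.6 and Section 13 with the opening of Section 10 and Section 10.2 on by-sequence presentation.

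The cost is SAP wording, some programming and one extra table from dates already collected. That table will hold few events: at 5% per day, 14 × (1 − exp(−0.10)) is about 1.3 participants per column.

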- e ECG will be completed on Days 2, 4, 6, and 12 only of multiple day periods during Treatment Sequence A.
- f During the OC+PSL Treatment Period, trough levels of PSL will be collected on morning before PSL dosing on Day 2, Day 4, Day 6, Day 8 and Day 10. Additional blood sampling for PK analysis will be taken on Day 12 (PSL PK) before (predose) and after PSL morning dose at 0.25h, 0.5h, 1h, 1.5h, 2h, 3h, 4h, 6h, 8h, 12h postdose and on Day 13 (PSL and OC PK) before (predose) and after the PSL and OC morning dose at 0.25h, 0.5h, 1h, 1.5h, 2h, 3h, 4h, 6h, 8h, 12h, 24h (before morning PSL dose on Day 14), and 48h (before morning PSL dose on Day 15) postdose.
- g During OC+PSL Treatment Period, blood sampling for OC PK analysis will be taken on Day 13 (before OC+PSL morning dose) and after PSL and OC morning dose at 0.25h, 0.5h, 1h, 1.5h, 2h, 3h, 4h, 6h, 8h, 12h, 24h (Day 14), 36h (Day 14), and 48h (Day 15) postdose. During the single-dose OC period, PK blood samples will be taken on Day 34 at predose and 0.25h, 0.5h, 1h, 1.5h, 2h, 3h, 4h, 6h, 8h, 12h, 24h (Day 35), 36h (Day 35), and 48h (Day 36) postdose.
- h Mitra™ (finger prick) blood samples will be taken at 0.5h, 1h, 3h, 6h, 12h postdose on Day 12 only for selected study participants.
- i The study participant can be discharged on Day 20 or Day 21, at the discretion of the principal investigator.

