### 3.9 Changes to protocol-defined analyses

- Changes in the name of analysis datasets (section 9.1 of the protocol):
  - The analysis set “Enrolled set” will be renamed as “All Study Participants” in the SAP and will correspond to all study participants who sign the informed consent form.
  - The analysis set “Pharmacokinetic Per Protocol Set (PK-PPS)” will be renamed as “Pharmacokinetic Set (PK Set)” in the SAP and will still correspond to the protocol definition of PK-PPS.
- For the purpose of the analysis of concomitant medications and adverse events 3 groups will be created, based on the treatment administered. The results will be presented for PSL alone, OC alone and the combination of PSL and OC.
- For the primary PK analysis, ping-pong plots have been added for EE and LN for  $C_{max}$ , and AUC for OC with and without PSL.
- Ping-pong plots have also been added for  $C_{max,ss}$  and  $AUC_{\tau}$ , for PSL and its two metabolites ( [REDACTED] and [REDACTED] ) for PSL with and without OC.
- Ping-pong plots have been added for  $C_{max,ss}$ ,  $AUC_{\tau}$ ,  $MR_{AUC_{\tau}}$ ,  $MR_{C_{max,ss}}$ ,  $CL_{ss}$ ,  $t_{1/2}$ , for PSL (with and without OC).
- Furthermore, the relationship between MR and  $C_{max}$  (with and without PSL) of EE and LN, and the exposure to PSL ( $AUC_{\tau}$ ) will be explored.
- Ctrough and MR based on  $AUC_{\tau}$  of PSL and its two metabolites, will also be compared between days (with OC [Day 13 for Sequence A and Day 30 for Sequence B] and without OC [Day 12 for Treatment Sequence A and Day 29 for Treatment Sequence B] using analysis of variance on the log-transformed parameters and estimation of geometric ratio of PK parameters between days with their 90% CI will be provided.
- Furthermore, the relationship between individual  $C_{max}$  (with and without PSL) of EE and LN and the exposure to PSL ( $AUC_{\tau}$ ) will be assessed by scatterplots and linear regression analyses.
- According to the protocol, the occurrence and incidence of AEs will be summarized by treatment sequence according to the intake of PSL (pretreatment or treatment-emergent) and

by intensity or relationship to PSL. As the relationship to PSL alone is not documented in the CRF, the relationship to study medication (PSL, PSL+OC, and OC) will be analyzed. Consequently, the definition of TEAE will be related to treatment (PSL, PSL+OC, or OC) and a TEAE will be attributed to a treatment according to the start date.

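### Does the late adverse-event rule in SAP 10.2 need rewriting because its hour and day limits disagree and follow-up events have no stated column?

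*SAP*

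**What the plan says.** SAP 10.2 attributes each adverse event (AE) to the treatment after which it starts. For Part 1, Sequence A, "all AEs starting after OC intake on Day 13 through Day 34 (prior to OC intake) will be attributed to PSL+OC", so the washout is carried forward with the preceding treatment, and "all AEs starting after OC intake on Day 34 through Day 41 will be attributed to OC". Sequence B mirrors this: OC alone runs from Day 1 to the first PSL dose on Day 18, and PSL+OC runs from Day 30 through Day 43. The paragraph then adds that "AEs starting more than 168 hours post last dose of study medication will be attributed to the SFU Period", and the schematic shows follow-up as Day 42 onward (A) and Day 44 onward (B).

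On display, SAP 3.9 says "The results will be presented for PSL alone, OC alone and the combination of PSL and OC", and SAP 3.6 names the same three groups. The appendix grid marks AEs under Treatment and Overall. SAP 10.2 elsewhere says that TEAEs are "summarized by MedDRA SOC, PT, treatment sequence and treatment period". The TEAE definition has a start (the first dose) and no end.

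SAP 1 restricts reporting to Part 1, and to a subset of the outputs.

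**The concern.** Three things look wrong on a first reading.

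- A limit in hours and a limit in whole days cannot both hold on Day 41 or Day 43, and no sentence says which governs. These are also the first days on which the safety follow-up visit may take place. The fixed days also fit poorly for someone who withdraws after the taper in Sequence A.
- The rule creates a fourth category, but the AE tables name three treatment groups. Because TEAEs have no end date, follow-up events are TEAEs, and TEAE incidence is a secondary endpoint. Two programmers might show or omit them.
- Washout events stay with the earlier treatment until the next dose, whereas events after the final dose stop at 168 hours. Equally late events can therefore land in different columns by sequence.

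At stake would be the reproducibility of the by-treatment AE tables and a fair reading across their columns.

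**Working it through.** **Inputs.** Last dose: OC on the morning of Day 34 (A); PSL, given twice daily, on Day 36 (B), so presumably in the evening. Last PSL dose in A: Day 19, evening. Follow-up visit: Day 41 to 44 (A), Day 43 to 46 (B), from SAP 3.2.2. AE recording runs until study completion or termination (SAP 10.2). Basis: 14 completers, 7 per sequence. Assumed, since the documents give no clock times: morning dose 07:00 to 10:00, evening dose 19:00 to 22:00, 12 hours apart.

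**1. The plan's day limits.** 168 h = 7 days; 34 + 7 = 41 and 36 + 7 = 43. The printed days are the 168-hour rule in calendar days for a participant on schedule.

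**2. Size of the hour/day disagreement.** Table 2-4 places the late OC samples at "24h (Day 35), 36h (Day 35), and 48h (Day 36) postdose". A 36 h sample still on Day 35 requires a Day 34 dose before noon. The 168 hours end at that clock time on Day 41.

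- A: 24 − 10 = 14 h to 24 − 7 = 17 h of Day 41 fall under both rules.
- B: 24 − 22 = 2 h to 24 − 19 = 5 h of Day 43.
- If the visit is held on Day 41 or 43, recording ends there, so the lower end can be zero.
- Maximum: 7 × 17 + 7 × 5 = 154 participant-hours = 6.4 participant-days.

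**3. Total time, by the hour rule.**

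| Window | A (days) | B (days) | Participant-days, 7 each |
|---|---|---|---|
| PSL alone | 12 | 12 | 84 + 84 = 168 |
| PSL+OC | 21 | 13.5 | 147 + 94.5 = 241.5 |
| OC alone | 7 | 17 | 49 + 119 = 168 |

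Total 577.5, so the overlap is at most 6.4 / 577.5 = 1.1%.

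**4. Withdrawal after the taper in A.** Day 19 evening + 7 days = Day 26 evening; from there to the morning of Day 34 is 7.5 days. This is a maximum. SAP 4.4 asks withdrawn participants back as soon as possible after the last dose, and recording stops at termination, so the range is 0 to about 7.5 days.

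**5. Follow-up TEAEs.** 44 − 41 = 3 and 46 − 43 = 3, so 0 to 3 days each, or at most 14 × 3 = 42 participant-days: 42 / (577.5 + 42) = 6.8%. Serious AEs are collected for up to 30 days after the end of the study (Protocol 8.4.1), so late ones can add to this.

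**6. Sequence difference.**

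- After the last PSL dose: 14.5 days in A against 7 in B, a gap of 7.5. With no cut and a visit 7 to 10 days after the last dose, the gap is 7.5 to 4.5.
- After OC alone: 17 days in B against 7 in A, a gap of 10. With no cut it is 10 to 7.

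For AEs collected up to the visit, the cut therefore accounts for 0 to 3 days; the rest follows from the washout and follow-up lengths. For example, an AE nine days after the last PSL dose is PSL+OC in A (Day 28) and follow-up in B (Day 45).

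**7. Would a uniform 168-hour limit per period be better?** It would move 7 × 7.5 = 52.5 (A) and 7 × 10 = 70 (B) participant-days to washout, leaving 168 / 189 / 98 in place of 168 / 241.5 / 168. The columns would cover less equal amounts of time than they do now.

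**The case for a change.** The best case for a change is that a few words would remove the ambiguity before programming. Withdrawals are a real prospect, since the protocol's summary of changes cites them as a reason for the amendment, and the Safety Set takes in anyone dosed once. No sentence says that Overall counts follow-up TEAEs. SAP 10.2 plans a table of non-serious TEAEs above 5%; with 14 participants one person is 1/14 = 7.1%, so a single late event could decide whether a term appears in a column. Concomitant-medication windows (SAP 6.4) run to Day 44 or 46 without a cut, so an AE and a medication starting together on Day 43 in Sequence A may be grouped differently.

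The wording gaps stand: two limits are printed, and the follow-up category has no stated column. The consequences claimed for them are weaker. An Overall column of TEAEs, with TEAEs defined without an end date, naturally includes follow-up events. The 5% example shows sensitivity only; the SAP does not say whether the threshold applies by column or whether that table is in the reported subset. The medication windows are a separate, stated classification. For a withdrawn participant, carrying events forward to a Day 34 dose that is never given makes little sense, so the hour rule is the evident choice. Whether sequence is shown is a layout question: the sequences are disjoint, so a table by sequence adds up to the one by treatment.

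**Conclusion.** No change is needed. SAP 10.2 leaves a detail that an analyst can settle sensibly in the table specifications, and neither choice alters a result. The hour/day disagreement is 0 to about 6.4 participant-days in all for participants on schedule (at most 1.1% of 577.5), plus 0 to about 7.5 days for any Sequence A participant who withdraws after the taper. The follow-up category covers 0 to 42 participant-days of scheduled follow-up. Carry-forward through washout is a defensible convention, and SAP 10.2 already prints every window by sequence, so a reader can see that they are unequal.

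Overall TEAE incidence is the same under either limit, no test compares the columns, and the primary pharmacokinetic analysis is untouched. The listings give sequence, onset date and time, and relative day, so any event can be re-sorted.

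This rests on reporting limited to Part 1, a basis of 14 completers (the Safety Set may be larger; its size is not given), the assumed clock times, and Overall counting all TEAEs as defined. The documents give no event rate and no number of withdrawals, so numbers of affected events cannot be estimated.
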